5.5 DRUG CONCENTRATION MEASUREMENTS AND PHARMACOKINETICS

5.5.1 Pharmacokinetic endpoint(s)

Pharmacokinetics will be a primary endpoint for the dose escalation part and a secondary endpoint for the biomarker specific MTD expansion cohorts/Phase II part. Extensive plasma PK sampling is therefore crucial in this trial. Whenever possible, a full plasma PK profile will be taken after first dose and at steady state (e.g. after 8 days of treatment with afatinib). An additional trough sample will be taken on day 15 to confirm steady state exposure to afatinib. In exceptional cases and only if paediatric patients are by no means able to undergo extensive plasma PK sampling a limited sampling approach should be applied.

In addition, in patients carrying a Rickham- or Ommaya reservoir, or undergoing lumbar puncture for clinical reasons not related to the trial, trough CSF sampling may be performed on day 8 or later to investigate CNS exposure to afatinib. This procedure is optional. The trough CSF PK sample must be accompanied by a trough plasma PK sample taken at the same time-point.

In any case, it must be attempted to keep all patients on their starting formulation for the first treatment course. This will be crucial for the MTD determination and PK assessment during first course.

In case patients' switch from tablet to liquid formulation or vice versa becomes necessary during treatment or if for any other reason (e.g. AE) plasma PK sampling cannot be performed as planned, plasma PK profiles may be obtained within treatment course 1 as deemed appropriate by the investigator and after consultation with the sponsor.

All details with respect to sampling procedures and time points are described in [Section 5.5.2](#) and tabulated in [Appendix 10.3](#).

Pharmacokinetics (PK) will be evaluated as follows:

- Non-compartmental analysis: PK parameters will include AUC, C_{max} , t_{max} and accumulation (or effective) half-life will be performed for all patients with extensive PK sampling
- Model-based analysis will be performed for all patients with sparse as well as extensive PK sampling

For further details regarding the PK analysis, please refer to [Section 7.3.5](#).

Proprietary confidential information.

© 2017 Boehringer Ingelheim International GmbH or one or more of its affiliated companies. All rights reserved.

This document may not - in full or in part - be passed on, reproduced, published or otherwise used without prior written permission.

5.5.2 Methods of sample collection

For quantification of afatinib plasma concentrations, 1 mL of venous blood will be taken in a K-EDTA (potassium ethylenediamine tetraacetic acid)-anticoagulant blood drawing tube at the blood sampling times indicated in [Appendix 10.3](#).

Determination of afatinib CSF concentrations will be performed from optional 1 mL samples taken via puncture of a Rickham- or Ommaya reservoir, or lumbar puncture conducted for clinical reasons not related to the trial, at the time-points specified in [Appendix 10.3](#). The type of the respective reservoir or lumbar puncture will be recorded in the eCRF.

Blood will be processed to plasma and all samples (plasma and CSF) further handled as described in the laboratory manual. This document gives all details about sample collection, preparation, storage and shipment.

All PK samples will be uniquely labelled with study number, subject number, visit number, and protocol (planned) time according to the time schedule in [Appendix 10.3](#). Would a patient discontinue treatment at the time of a PK sampling, the sample(s) taken at this visit may need to be renamed for the EOT visit.

Pharmacokinetic samples will only be used for the analyses as described in the Clinical Trial Protocol. The plasma and CSF samples will be discarded at the latest when the CTR has been signed.

Correct sample handling as well as correct and complete documentation of drug administration and blood/CSF sampling is mandatory to obtain data of adequate quality for the pharmacokinetic analysis.

Date and time of pharmacokinetic sampling should be recorded on the eCRF. In addition, the dose, date and time of afatinib administration and time of food intake before and after medication for the four (4) days prior to pharmacokinetic sampling should be recorded in the eCRF.

5.5.3 Analytical determinations

Plasma and CSF concentrations of afatinib will be determined by validated HPLC-MS/MS assays (high performance liquid chromatography, tandem mass spectrometry) at an appropriate bioanalytical laboratory e.g.

. If necessary individual patient plasma samples may be analyzed on an „ad hoc” basis.

5.6

Proprietary confidential information.

© 2017 Boehringer Ingelheim International GmbH or one or more of its affiliated companies. All rights reserved.

This document may not - in full or in part - be passed on, reproduced, published or otherwise used without prior written permission.

Proprietary confidential information.

© 2017 Boehringer Ingelheim International GmbH or one or more of its affiliated companies. All rights reserved.

This document may not - in full or in part - be passed on, reproduced, published or otherwise used without prior written permission.

Proprietary confidential information.

© 2017 Boehringer Ingelheim International GmbH or one or more of its affiliated companies. All rights reserved.

This document may not - in full or in part - be passed on, reproduced, published or otherwise used without prior written permission.

5.6.1 Endpoints based on biomarker(s)

The objective response level obtained from the biomarker selected MTD expansion cohorts/Phase II part must be considered meaningful by experts in the field of paediatric oncology. For further details refer to [Section 7.6](#).

5.6.2 Methods of sample collection

Sample analyses and logistics will be performed by a
certified central laboratory, after validation of assay procedures.

Tissue sample from archived tumour blocks is preferred. Alternatively, a minimum of 15 up to 20 slides of 4 µm thickness should be provided. Further details are provided in the ISF.

Data transfer agreements, data storage and analysis will be handled by BI.

5.6.3 Analytical determinations

Refer to [section 5.6.1](#)

5.7 PHARMACODYNAMICS

Not applicable

5.7.1 Pharmacodynamic endpoints

Not applicable

5.7.2 Methods of sample collection

Not applicable

5.8 PHARMACOKINETIC - PHARMACODYNAMIC RELATIONSHIP

Correlation between drug concentration and response may be made if appropriate data are available. In addition, exploratory correlation will also be made between drug concentration and AEs.

6. INVESTIGATIONAL PLAN

6.1 VISIT SCHEDULE

After the screening visit, patients will have to come to the investigational site on the days provided in the [Flow Chart](#). More visits can be performed if deemed necessary by patient, caregivers and/or investigator. As soon as the treatment with afatinib will be permanently discontinued, the patient has to undergo the end of treatment visit (i.e within 7 days of last afatinib administration). A last visit will be performed at the end of the residual period (i.e. 28-30 days after the last afatinib administration) for safety follow-up. This last safety follow-up visit will represent the end of trial visit for the patient. Thereafter, regular contacts (every 12 weeks) after the end of trial visit will be done either via phone/correspondence to collect information whether the patient is still alive.

6.2 DETAILS OF TRIAL PROCEDURES AT SELECTED VISITS

6.2.1 Screening period

The screening period may be as long as 28 days between signing informed consent and first administration of the trial drug. The screening period may be longer in case of administrative issues and/or if the patient would have to recover from an intercurrent disease.

During the screening period, the following actions will be performed:

Before screening period	Applies only to MTD expansion cohorts/Phase II part: Where requested, a pre-screening informed consent may be used allowing only for collection and testing of tumour tissue for ErbB deregulation (see Section 4.1.2). If tested positive for ErbB selection biomarkers, parents /legal guardian have to sign an informed consent –and patients have to assent in order to be entered into this trial and proceed with trial procedures (see below).
Informed consent	An informed consent has to be given by the parents /legal guardian and assent by the patient by using a suitable informed consent for the respective age group.
Demographics	
Medical and oncological history	For details refer to Section 5.2.5
Vital signs and physical examination	Preferably be done by the same person throughout the trial for a respective patient if feasible
Ophthalmological examination	To exclude keratitis
Pulmonary examination	To exclude ILD
Height and weight	Height in cm and weight in kg
Performance score	To be assessed using Lansky score for the patients aged ≤ 12 years and the Karnofsky score for the patients aged >12 years at time of informed consent
Planned hospital stay	Any stays in hospital that are planned to be performed during the trial shall be reported
Check of inclusion and exclusion criteria	To assess eligibility of the patient
Pregnancy test	To be performed in post-menarchal female patients who are of childbearing potential and within 7 days prior to first treatment.
Cardiac assessment	
 LVEF echocardiography shall be performed and the results must be

Proprietary confidential information.

© 2017 Boehringer Ingelheim International GmbH or one or more of its affiliated companies. All rights reserved.

This document may not - in full or in part - be passed on, reproduced, published or otherwise used without prior written permission.

	
documented in source data and eCRF
 
 12 lead-ECG as detailed in Section 5.2.4
Blood sampling for safety lab	
Blood collection for assessment of the parameters as described in Section 5.2.3. In case the safety lab parameters as outlined in Section 5.2.3 have been collected within the past 7 days prior signing informed consent, the data may be reported in the eCRF and no new blood needs to be collected during screening

Assessment of the tumour disease	
Depending on the tumour type, an assessment of the tumour disease has to be reported in the eCRF based on:
 
 imaging findings tumour markers in blood or urine if indicated bone marrow if indicated 
Tumour assessment does not need to be repeated at the screening visit if there are valid results available from assessments which were performed as part of routine clinical practice within the allowed time window (within 28 days prior to start of treatment).

Tumour tissue	
-Dose finding part: confirm tumour tissue availability for retrospective biomarker testing or provide evidence of ErbB pathway deregulation -MTD expansion cohort: provide tumour tissue for prospective biomarker testing of ErbB pathway deregulation – see Section 5.6

Concomitant therapies	See Section 4.2.1
Adverse events	All AEs occurring since the signature of the informed consent - See Section 5.2.2
Dose assessment	Confirmation of dose according to dose level and BSA

6.2.2 Treatment period(s)

COURSE 1

Visit 1 (day 1)

The very first intake of afatinib will take place on day 1 of course 1. Patients may stay in hospital for the day 2 assessments such as blood sampling for safety laboratory and pharmacokinetics if applicable and if considered necessary by the investigator.

Before the first intake of afatinib, the following assessments shall be done:	
Vital signs and physical examination	Preferably be done by the same person throughout the trial for a respective patient if feasible
Weight	
Performance score	Lansky for patients ≤ 12 years or Karnofsky for patients older than 12 years at time of informed consent
Quality of life questionnaire	For MTD expansion cohorts/Phase II part only
Blood sampling for safety lab	Not to be older than 48 hours before the trial drug intake
Blood for the baseline pharmacokinetic	Pre-dose sample to be collected about 5 minutes before afatinib intake, see Appendix 10.3
Concomitant therapies	Update if applicable
Adverse events	Update if applicable
Dispense trial drug	The allocated treatment kit(s) should be dispensed to the patient/parent(s)/caregiver for the first drug intake at site followed by the daily intake along this treatment course.

Proprietary confidential information.

© 2017 Boehringer Ingelheim International GmbH or one or more of its affiliated companies. All rights reserved.

This document may not - in full or in part - be passed on, reproduced, published or otherwise used without prior written permission.

After first drug intake:	
Blood for pharmacokinetics post dose	To be collected on day 1 at 1, 2, 3, 4, 5, 6, 8 hours after afatinib intake as described in Section 5.5.2 and at the time points tabulated in Appendix 10.3 . It is of utmost importance to report the exact clock time of the first trial drug intake and the actual sampling date and time for blood samples in the eCRF. In exceptional cases and only if patients are by no means able to undergo extensive PK sampling, a limited sampling approach should be applied with blood sampling before, 1h and 3 h after afatinib administration. For further details see Section 5.5.2 and Appendix 10.3 .

Visit 1 (day 2)

Repeated procedures	Physical examination and vital signs; update on concomitant therapies and adverse events
Blood for pharmacokinetic	For extensive PK sampling, samples to be collected 24 hours after afatinib intake. Patients (or parents and/or legal guardian) should be instructed not to take the trial medication prior to the 24h blood sample. The trial medication must be taken after the last PK blood sample has been drawn
Drug intake	Intake of the trial drug should take place at the same time as previous day
Patient diary	Check for completion

Visit 2 (day 8)

Repeated procedures	Physical examination and vital signs; weight; blood sampling for safety lab (limited); update on concomitant therapies and adverse events
Cardiac assessment	12 lead-ECG as detailed in Section 5.2.4
Blood for pharmacokinetics pre-dose at steady state	Pre-dose sample to be collected about 5 minutes before afatinib intake, see Appendix 10.3
Drug intake	
blood for pharmacokinetic post dose at steady state	Extensive PK sampling: blood has to be collected at 1,2,3,4,5,6,8 and 24 hours after afatinib intake (refer to Appendix 10.3). Patients (or parents and/or legal guardian) should be instructed not to take the trial medication prior to the 24h blood sample (day 9). The trial medication must be taken after the last PK blood sample has been drawn. In exceptional cases and only if patients are by no means able to undergo extensive PK sampling, a limited sampling approach should be applied with blood sampling before, 1h and 3 h after afatinib administration. For further details see Section 5.5.2 and Appendix 10.3 .
Patient diary	Check for completion
Compliance check	Check on trial drug compliance

Visit 3 (day 15)

Repeated procedures	Physical examination and vital signs; weight; blood sampling for limited safety lab; update on concomitant therapies and adverse events
Blood for pharmacokinetics pre-dose to confirm steady state	Pre-dose sample to be collected about 5 minutes before afatinib intake, see Appendix 10.3

Proprietary confidential information.

© 2017 Boehringer Ingelheim International GmbH or one or more of its affiliated companies. All rights reserved.

This document may not - in full or in part - be passed on, reproduced, published or otherwise used without prior written permission.

Patient diary	Check for completion
---------------	----------------------

Visit 4 (day 22)

Repeated procedures	Physical examination and vital signs; weight; blood sampling for limited safety lab; update on concomitant therapies and adverse events
Patient diary	Check for completion

COURSE 2

Visit 1 (day 1)

This visit should take place at day 29 from start of treatment and should serve for confirming patient's eligibility for treatment continuation

- Depending on the patient status, the investigator has to perform a disease assessment on patient's eligibility for the next treatment course. This might include but is not limited to:
 - Imaging findings (requested only every 2 courses: course 3 visit1, C5V1, C7V1...)
 - Tumour markers in blood or urine if indicated
 - Bone marrow if indicated

In case treatment discontinuation is required at this visit, please complete the EOT visit instead of this visit.

For patients included in the dose escalation part, a DLTs evaluation should be provided before to start a new course of treatment.

C2V1 visit should include:

Patient acceptability	Completion of acceptability questionnaires by patients, parents/caregiver and investigator/site staff Special note: at any time, if the patient switches from his/her initial formulation to the other, the questionnaires should be completed again after 28 days of intake of the new formulation.
Quality of life questionnaire	For MTD expansion cohorts/Phase II part only
Repeated procedures	Physical examination and vital signs; weight; blood sampling for safety lab; update on concomitant therapies and adverse events
Performance score	Lansky for patients ≤ 12 years or Karnofsky for patients older than 12 years at time of informed consent
Cardiac assessment	LVEF echocardiography shall be performed and the results must be documented in source data and eCRF for DLT evaluation
Patient diary	Check for completion
Compliance check	Check on trial drug compliance
Eligibility for treatment continuation	Confirm eligibility for further treatment
If the patient eligibility for further treatment is confirmed:	
Dose assessment	Assess appropriateness of the afatinib dose
Dispense trial drug	New afatinib kit(s) must be dispensed to the patient/parent(s)/legal guardian

Proprietary confidential information.

© 2017 Boehringer Ingelheim International GmbH or one or more of its affiliated companies. All rights reserved.

This document may not - in full or in part - be passed on, reproduced, published or otherwise used without prior written permission.

	(recalculate BSA for allocation of dose) for a daily drug intake along this treatment course
--	--

Visit 2 (day 15)

Repeated procedures	Physical examination and vital signs; weight; blood sampling for limited safety lab; update on concomitant therapies and adverse events
Dose assessment	Assess appropriateness of the afatinib dose

COURSE 3 AND ONWARDS

Visit 1 (day 1)

Repeated procedures	Physical examination and vital signs; weight; height (every other course); blood sampling for safety lab; update on concomitant therapies and adverse events
Quality of life questionnaire	For MTD expansion cohorts/Phase II part only
Performance score	Lansky for patients \leq 12 years or Karnofsky for patients older than 12 years at time of informed consent
Cardiac assessment (every 3 rd course)	
 • LVEF echocardiography • 12 lead-ECG as detailed in Section 5.2.4
Patient diary	Check for completion
Compliance check	Check on trial drug compliance
Tumour assessment	Imaging assessment every 8 weeks, tumour markers where indicated
Eligibility for treatment continuation	Confirm eligibility for further treatment
If the patient eligibility for further treatment is confirmed:	
Height measurement	Every 2 courses
Dose assessment	Assess appropriateness of the afatinib dose
Dispense trial drug	New afatinib kit(s) must be dispensed to the patient/parent(s)/legal guardian (recalculate BSA for allocation of dose) for a daily drug intake along this treatment course

6.2.3 End of treatment and follow-up period

End Of Treatment visit

This visit will take place as soon as a decision is made to permanently discontinue trial treatment.

The EOT visit will include the following actions:

Repeated procedures	Physical examination and vital signs; blood sampling for safety lab; update on concomitant therapies and adverse events
---------------------	---

Proprietary confidential information.

© 2017 Boehringer Ingelheim International GmbH or one or more of its affiliated companies. All rights reserved.

This document may not - in full or in part - be passed on, reproduced, published or otherwise used without prior written permission.

Ophthalmological examination	To exclude keratitis
Pulmonary examination	To exclude ILD
Pregnancy test	To be performed in post-menarchal female patients who are of childbearing potential
Performance score	Lansky for patients \leq 12 years or Karnofsky for patients older than 12 years at time of informed consent
Cardiac assessment	
 • LVEF echocardiography • 12 lead-ECG as detailed in Section 5.2.4
Assessment of the tumour disease	Depending on the tumour type, an assessment of the tumour disease has to be reported in the eCRF based on: 
 ○ imaging findings ○ tumour markers in blood or urine if indicated ○ clinical findings ○ bone marrow if indicated
Patient diary	Check for completion
Compliance check	Check on trial drug compliance
Conclusion of treatment	To confirm permanent treatment discontinuation

Follow-up visit for safety (28-30 days after last afatinib intake)

Safety update	Update on concomitant therapies and adverse events
Conclusion of patient participation	Confirmation of trial discontinuation for the patient

6.2.4 Observational period

The observational period is a post-trial period for data collection on vital status. The site will contact patients/parent(s)/legal guardian or patients' health care providers to collect patients' vital status every 12 weeks. Death information from public sources, e.g. death registry, obituary listing, etc. can also be used when it is available and verifiable.

The data should be documented in the patient's chart.

Adverse events/serious AEs should still be reported in this period if they are considered relevant by the investigator.

The whole trial will end when the last patient has completed the 28-30 day FU visit.

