Informed consent /patient assent	x ⁵											
Demographics	x											
Medical history	x											
Physical examination including neurological exam in patients with brain tumours	x	x	x	x	x	x	x	x	x	x		
Ophthalmologic examination	x									x		
Pulmonary examination ⁶	x	x					x		x	x		
Performance score ²²	x	x					x		x	x		
Vital signs	x	x	x	x	x	x	x	x	x	x		
Height ⁷	x								x ⁷			
Weight	x	x		x	x	x	x	x	x			
Safety laboratory tests ⁸⁻⁹	x	x ⁸		x ⁹	x ⁹	x ⁹	x	x ⁹	x	x ⁸		
Pregnancy test (if appl.) ¹⁰	x									x		
12 lead-ECG ¹¹	x			x					x ¹¹	x		
LVEF echo	x						x		x ¹²	x		
Disease assessment imaging ¹³	x								x ¹³	x		
Tumour marker(s) ¹⁴	x						x		x	x		
Tumour sample tissue availability ²³	x											
Review in-/ex- criteria	x											
Dose assessment	x						x ¹⁵	x ¹⁵	x ¹⁵			
Dispense trial drug ¹⁶		x					x		x			
Afatinib administration		Continuous oral once daily, fasted										
Pharmacokinetics		x ¹⁷	x ¹⁷	x ¹⁷	x ¹⁷							
Adverse events	x	x		x	x	x	x ¹⁸	x	x	x	x	x ¹⁹
Concomitant therapies	x	x		x	x	x	x	x	x	x	x	
Compliance check				x			x		x	x		
Patient diary check			x	x	x	x	x		x	x		
Eligibility for treatment continuation							x		x			
Conclusion of treatment										x		
Conclusion of patient participation											x	
Survival status												x

- All courses are of 4 weeks duration (28 days). Day 1 of a new course should take place on day 29. Patients may continue on treatment for unlimited courses until the criteria for stopping medication are met (see [Section 3.3.4](#)). Visits are performed weekly for the first course. At course 2, visits will take place every 2 weeks ([Visit 2 day 8](#) and visit 4 day 22 are no longer requested). From course 3 onwards, only visits “1” are required.
- EOT= end of treatment – When the decision is taken to permanently discontinue the study medication, the EOT visit must be performed within 7 days after last administration of afatinib. If the decision is taken at a scheduled visit, the EOT visit will be performed instead of the scheduled visit. Examinations performed at this time may need to be renamed for the actual visit conducted.
- FU= safety follow-up 28 to 30days after last afatinib administration. With the FU visit the patient will have completed his/her trial participation.
- OP= observation (post-trial) period. Collection of information on vital status every 3 months. Information could be collected from the patient’s notes or by telephone contact. A formal visit is not required.

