3.3.4 Removal of patients from therapy or assessments

3.3.4.1 Removal of individual patients

The Investigator, patient and/or parent/legal guardian may stop study treatment at any time for safety or personal reasons.

If a patient is entered in violation of inclusion/exclusion criteria, the sponsor, in discussion with the investigator and if needed DMC, will determine the medical benefit/risk on a patient-by-patient basis and can require such a patient be discontinued from the study treatment.

A patient is to discontinue study medication if:

- 1 The patient and/or parent/legal guardian withdraw assent/consent to continue therapy without the need to justify.
- 2 The patient is no longer receiving benefit from treatment, in the opinion of the investigator.
- 3 In the investigator's medical judgment, further participation would not be in the best interest of the patient, or might be injurious to the health and well-being of the patient
- 4 The patient is no longer able to participate for other medical reasons (e.g. surgery, adverse events, secondary malignancy, or other diseases)

Proprietary confidential information.

© 2017 Boehringer Ingelheim International GmbH or one or more of its affiliated companies. All rights reserved.

This document may not - in full or in part - be passed on, reproduced, published or otherwise used without prior written permission.

- 5 A female post-menarchal patient becomes pregnant ([Section 5.2.2.3](#))
- 6 The patient is diagnosed with ILD, keratitis or heart failure (including clinically relevant LVEF reduction) ([Section 4.2.1](#))
- 7 The patient needs further dose reductions considered necessary but not allowed according to the protocol ([Section 4.1.4.3](#))

The sponsor may remove patients from the study after completion of the primary analysis and grant access to afatinib via an alternative source e.g. through an expanded-access program, named patient use program, or compassionate use protocol.

Patient discontinuation of study participation:

A patient, who has discontinued study medication, will complete a follow-up (FU) visit 28-30 days after the last intake of the trial drug. After this FU visit, no further study procedure will be performed and the patient will enter the observation period during which only data collection on (S)AE(s) considered relevant by investigator, vital status and further anti-cancer treatment will be requested.

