4.2 CONCOMITANT THERAPY, RESTRICTIONS, AND RESCUE TREATMENT

4.2.1 Rescue medication, emergency procedures, and additional treatment(s)

Rescue medication

Rescue medications to reverse the actions of afatinib are not available. There is no specific antidote for overdosage with afatinib. Potential adverse events should be treated symptomatically. In cases of suspected overdose, afatinib should be withheld and supportive care initiated. If indicated, elimination of unabsorbed afatinib may be achieved by emesis or gastric lavage.

Common adverse events of afatinib treatment observed in adults with specified management recommendations and/or requirements include diarrhoea, mucositis and rash/acne. To improve tolerability and the probability of clinical benefit, patients should receive prompt and appropriate supportive care at the first signs of symptoms. Suggested treatments for AEs are described below.

Concomitant treatments

Concomitant medications or therapy to provide adequate supportive care may be given as clinically necessary.

After study enrolment, palliative radiotherapy may be given for bone pain or for other reasons (e.g. bronchial obstruction, skin lesions), provided that the total dose delivered is in a palliative range according to institutional standards. The irradiated area must not be used for tumour response assessment. During palliative radiotherapy, study treatment should be paused and be resumed once the patient has recovered from any radiation associated toxicity. If medication is interrupted for more than 14 days, the decision to continue will be made by the BI clinical monitor in agreement with the investigator. Continuous interruption of >28 days due to palliative radiotherapy will not be allowed.

All concomitant therapies, including anaesthetic agents (except pre-planned anaesthetic agents e.g. related to imaging exams), vitamins, homeopathic/herbal remedies, nutritional supplements, must be recorded in the eCRF during the screening and treatment period, starting from the date of signature of informed consent for trial participation, and ending at the EOT visit. After the EOT visit, only concomitant therapy indicated for treatment of an AE has to be reported.

In case of major surgery (as judged by the investigator), it is recommended to stop treatment with afatinib around one week prior to the surgery, and to restart treatment after complete

Proprietary confidential information.

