Progressed according to radiological assessment, i.e. longer than 112 days between progression and last assessment before progression.	censored	Date of last radiological assessment before progression
Alive and not progressed (irrespective of missed radiological assessments)	censored	Date of last radiological assessment
Initiation of subsequent anti-cancer therapy		
Subsequent anti-cancer therapy started before progression or death	censored	Date of last radiological assessment before subsequent anti-cancer therapy
No baseline and/or post-baseline imaging and subsequent anti-cancer therapy started prior to a death	censored	Date of first treatment administration

For further details on endpoints, please see CTP Section 5.

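### Protocol passages disagree on recording anti-cancer therapy after afatinib, and SAP Table 5.2.2:1 uses its start to decide whether some deaths are censored or events in PFS and DoR

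*Protocol*

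**What the plan says.** Five places in the protocol bear on what is collected once afatinib stops.

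- **Section 3.3.4.1**, for the observation period after the follow-up (FU) visit: "only data collection on (S)AE(s) considered relevant by investigator, vital status and further anti-cancer treatment will be requested".
- **Section 6.2.4**, for the same period: "The observational period is a post-trial period for data collection on vital status". It adds adverse events the investigator judges relevant, and says the data go into the patient's chart.
- **Flow chart, footnote 4**: "Collection of information on vital status every 3 months". The observation column is marked for adverse events and survival status. The concomitant-therapy row stops at the FU visit.
- **Section 6.1**: the 12-weekly contacts serve "to collect information whether the patient is still alive".
- **Section 4.2.1**: "After the EOT visit, only concomitant therapy indicated for treatment of an AE has to be reported".

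SAP Table 5.2.2:1 has a row headed "Subsequent anti-cancer therapy started before progression or death". Its outcome is censoring, dated to the last radiological assessment before that therapy. A companion row covers patients without baseline or post-baseline imaging and censors them at first dose. Without recorded subsequent therapy, a death without progression is an event if it falls within 112 days of the last assessment, and is censored if later. SAP Section 5.2.2 applies the same rules to DoR where applicable. The protocol's own PFS definition (Section 5.1.1.2) has no subsequent-therapy rule. The SAP history table dates the PFS censoring rules to July 2020, after the June 2017 protocol revision.

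**The concern.** The SAP rule depends on an item that one protocol section requests and the visit schedule does not list. A site working from the flow chart and Sections 6.1 and 6.2.4 could record vital status and nothing about the next line of treatment. In the analysis, therapy that was never asked about then looks the same as therapy that was never given.

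The patients exposed are those who stop without documented progression, for example after an adverse event, withdrawal of consent or exhausted dose reductions (Section 3.3.4.1). For them, Section 3.3.4.1 adds: "After this FU visit, no further study procedure will be performed". Death is then the main PFS event that can still be observed, and whether it counts depends on whether the new therapy was written down. If practice differs between sites, the PFS estimate mixes two definitions. One censors at new therapy and the other ignores it.

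**Working it through.** **1. The SAP's window.** Imaging is every 8 weeks, and the rule allows at most one missed assessment: 2 × 8 × 7 = 112 days. The SAP figure reproduces.

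**2. One patient under both readings.** Assume the last progression-free scan is on day 56 and new therapy starts 18 days later, on day 74. The window closes on day 56 + 112 = 168.

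| Death on day | Days after scan | Therapy recorded | Therapy not recorded |
|---|---|---|---|
| 100 | 44 | censored, day 56 | event, day 100 |
| 140 | 84 | censored, day 56 | event, day 140 |
| 168 | 112 | censored, day 56 | event, day 168 |
| 169 | 113 | censored, day 56 | censored, day 56 |

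Only deaths after the therapy starts and inside the window change status. If afatinib stopped near day 56, the FU visit (28 to 30 days after the last dose) falls around days 84 to 86. Therapy on day 74 is then in the EOT-to-FU interval, where Section 4.2.1 is the relevant text. Therapy after the FU visit brings Section 3.3.4.1 into conflict with 6.2.4. The classification problem is the same in both intervals.

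**3. Share of exposed patients who could change status.** Protocol Section 1.1 quotes survival of 4 to 6 months from relapse in high-grade glioma. As an assumption, read this as an exponential median counted from the last scan, with 30.4 days per month. The share dying between day 18 and day 112 after the scan is 2^(−18/m) − 2^(−112/m).

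- m = 5 months (152 days): 0.921 − 0.600 = 0.321, about 32%.
- m = 6 months (182.4 days): 0.934 − 0.653 = 0.281, about 28%.
- m = 4 months (121.6 days): 0.902 − 0.528 = 0.374, about 37%.

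**4. Number of patients.** The expansion part has up to 38 patients. Assume that 15 to 35% stop without progression and that 50 to 80% of those would start new therapy if alive at that point. The documents give neither rate.

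- Low: 38 × 0.15 × 0.50 × 0.321 = 0.9.
- High: 38 × 0.35 × 0.80 × 0.321 = 3.4.

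This is about 1 to 3 patients. With the 28% and 37% shares, the extreme corners are 0.8 and 4.0.

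**5. Effect on 24-week (day 168) PFS.** Illustration on assumed data: 38 patients, 20 progressing at day 56, 8 at day 112, k such deaths at day 140 with the last scan at day 56, and the rest censored at day 168. Kaplan-Meier estimates:

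- Not recorded: (10 − k)/38.
- Recorded: (18/38) × (10 − k)/(18 − k), because the k patients leave the risk set at day 56.

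| k | Not recorded | Recorded | Difference (points) |
|---|---|---|---|
| 1 | 23.7% | 25.1% | 1.4 |
| 2 | 21.1% | 23.7% | 2.6 |
| 3 | 18.4% | 22.1% | 3.7 |

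For k = 4, the extreme corner in step 4, the figures are 15.8% and 20.3%. All rows compare every therapy recorded with none recorded. Variation between sites would give less.

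**The case against.** The best reply is that silence is not contradiction. Section 3.3.4.1 is the only text that says what is requested about anti-cancer treatment after the FU visit, and it does request it. The vital-status passages are not exhaustive, since 6.2.4 itself adds adverse events. Section 4.2.1 speaks of concomitant therapy, and the next line of treatment after afatinib is arguably not concomitant. The eCRF is not among the documents, and a mandatory field would remove the variation between sites.

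Much of this stands. A reader might infer that the SAP rule cannot be applied at all. The documents do not support that, because 3.3.4.1 asks for the data and the form is unseen. A reader might also infer that the SAP censors on the therapy start date, but that date only triggers censoring at the preceding scan.

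The reply does not settle which text a site follows. The flow chart and Sections 6.1 and 6.2.4 form the working schedule, and none of them lists the item. The request in 3.3.4.1 begins only after the FU visit, so it does not clearly cover therapy started between EOT and FU.

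The effect is also small against sampling error. For a PFS rate of 25% in 38 patients, the standard error is √(0.25 × 0.75/38) = 7.0 points, or about ±14 points for a 95% interval. That limits the importance of the point, but an avoidable classification error remains.

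**Conclusion.** The protocol passages are inconsistent, and the inconsistency reaches the analysis. A death after new therapy, without documented progression and within 112 days of the last scan (or of treatment start if there is no post-baseline scan), is censored or an event according to whether the therapy was recorded. On the assumed rates this concerns about 1 to 3 of 38 patients and at most a few points of 24-week PFS, as an all-versus-none upper bound.

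The size rests on rates that the documents do not give, and on a glioma survival range extended to all tumour types. Counting every death in the window would overstate it: 1 − 2^(−112/152) = 40%, but deaths before the new therapy starts cannot change status.

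A wider reading, that the trial's efficacy result is in doubt, is not supported. The primary endpoint, objective response, does not use this rule. Patients whose progression is documented before any new therapy are unaffected. PFS and DoR are secondary and descriptive, and DoR is only listed if fewer than 5 patients respond (SAP Section 7.5.2). The point is worth correcting because the remedy is cheap.

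**What to change.** **Protocol.** Reconcile Section 4.2.1, flow chart footnote 4, Section 6.1 and Section 6.2.4 with 3.3.4.1. For every patient, record in the eCRF the start date and type of the first anti-cancer therapy after afatinib, from EOT through the FU visit and at each 12-weekly contact.

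**SAP.** Add a sensitivity analysis of PFS, and of DoR if it is estimated, that ignores subsequent therapy for all patients. This applies one definition to everyone and does not need the therapy date. List the patients whose subsequent-therapy status is unknown. Restricting the subsequent-therapy rows to patients with known status would not be enough, because patients of unknown status would stay under the ordinary death rule and the two definitions would remain mixed.

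**Cost.** One extra question at contacts that already take place, a little more site data entry, aligned wording in four protocol passages, and one additional analysis with a listing.
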